## 10.3. Assessments

Note: For the various questionnaires that are used during this study, at each time point where a questionnaire is being completed there must be no reference back to previous questionnaires that have been completed by that subject during the study.

### 10.3.1 Efficacy

#### 10.3.1.1 Western Ontario and McMaster Universities Osteoarthritis Index

The WOMAC LK version 3.1 is the most recent version of this instrument for the assessment of hip and knee OA. The WOMAC Osteoarthritis Index is widely used to measure pain, stiffness, and physical function in subjects with OA pain. It is considered to be a reliable and valid instrument for this indication.

Subjects will rate each of scales for Pain, Stiffness, and Physical Function over the past 24 hours. The WOMAC questionnaire will be completed for the target knee. The scores will be recorded in the eCRF.

The WOMAC Pain scale evaluates the following 5 items:

Each item is rated on a scale of 0 to 4, with 0 being no difficulty and 4 being extreme difficulty (None = 0, Mild = 1, Moderate = 2, Severe = 3, Extreme = 4).

[figure not shown]
The WOMAC Stiffness scale assesses 2 items:

Each item is rated on a scale of 0 to 4, with 0 being no difficulty and 4 being extreme difficulty (None = 0, Mild = 1, Moderate = 2, Severe = 3, Extreme = 4).

The WOMAC Physical Function assesses the following 17 categories using the 0 to 4 scale (None = 0, Mild = 1, Moderate = 2, Severe = 3, Extreme = 4) described previously:

The **WOMAC Composite score** is most commonly calculated by summing the items for all 3 subscales. Higher scores on the WOMAC indicate worse pain, stiffness, and functional limitations. The total score is calculated as follows: Total score = /96 = \_\_\_\_%

#### 10.3.1.2 Patient Global Assessment

The PGA is a self-administered instrument that measures the subject's overall impression of their OA pain in their target knee on a 5-point scale where 0 = "Very Good" and 4 = "Very Poor". The scores will be recorded in the eCRF.

Subjects will be asked to complete the following statement:

"How would you rate your osteoarthritis condition over the last 24 hours?"

The response options include the following:

Very Good	0
Good	1
Moderate	2
Poor	3
Very Poor	4

#### 10.3.1.3 Patient Global Impression of Change

The PGIC is a self-administered instrument that measures change in subjects' overall improvement with treatment on a scale where 1 = "very much improved" and 7 = "very much worse." The scores will be recorded in the eCRF. Subjects will be asked the following question: "How would

you rate your overall improvement with treatment during the clinical trial?" The response options include the following:

Very Much Improved	1
Much Improved	2
Minimally Improved	3
No Change	4
Minimally Worse	5
Much Worse	6
Very Much Worse	7

#### 10.3.1.4 Numeric Rating Scale

The NRS is an 11-point scale from 0 to 10. On this scale, 0 = no pain and 10 = the worst pain imaginable. NRS 11-point scale will be assessed in 2 ways. One is the average pain condition over the last 24 hours, and the other is the worst painful condition over the last 24 hours.

The subject will rate his or her target knee average and worst pain intensity when they replace a patch and before taking any rescue medication on the day using the following question: "On a scale from 0 to 10, where "zero" represents "no pain" and "10" represents "the worst possible pain," how would you rate the average / worst pain that you have been feeling in your knee over the last 24 hours?"

**Note:**

1. The average pain scale (not worst) will be used for the eligibility confirmation of inclusion criteria and identifying the target knee.
2. The NRS pain assessment must be performed daily by the subject at home between Screening (V1) and the start of the Washout Period.

[REDACTED] will be entered to the eCOA system and the mean NRS scores will be calculated for subjects to be considered eligible for study participation.

3. The subject will continue assessing and recording the NRS pain score daily at home during the Washout Period.

[REDACTED] will be entered to the eCOA system and the mean NRS scores will be calculated for subjects to be considered eligible for study participation.

### **10.3.1.5 Use of Rescue Medication**

If needed, subjects will be allowed to take up to a maximum of 2 g (4 × 500 mg tablets) of oral APAP per day (as provided by the Sponsor or designee) as rescue medication for the treatment of the target knee pain of OA because of lack of efficacy of study drug (not for the non-target knee) if the subject does not feel enough pain relief by the study drug, any other aches they might experience during the trial such as headache and reduction of fever except within 3 calendar days prior to the Baseline Visit, on the day of Baseline Visit (V3), from Baseline Visit until Visit 4, within 2 calendar days prior to all subsequent visits (V5, V6, V7, and V8), and on the day of the clinic visits (V4, V5, V6, V7, and V8). Information regarding the use of rescue medication, such as the number of tablets, the time and the reason of use, will be recorded on the appropriate concomitant medication eCRF. Subjects should not use OTC APAP as rescue medication.

### **10.3.2 Safety**

Safety assessments will include the evaluation of laboratory assessments, vital signs, 12-lead ECGs, physical examinations, dermal safety assessments and AEs.

#### **10.3.2.1 Laboratory Safety Assessments**

##### **10.3.2.1.1 Laboratory Tests to be Performed**

Samples for the following laboratory tests will be collected at the time points specified in the schedule of events (see [Section 10.2](#)).

---

Hematology:	Hemoglobin, hematocrit, red blood cell (RBC) count, RBC indices, mean corpuscular hemoglobin, mean corpuscular hemoglobin concentration, platelet count (or estimate), white blood cell count including differential.
Serum chemistry:	Albumin, total bilirubin, direct bilirubin, total protein, calcium, alkaline phosphatase, alanine aminotransferase, aspartate aminotransferase, $\gamma$ -glutamyltransferase, blood urea nitrogen, creatinine, fasting glucose and total lipids (8 to 10 hours after fasting is required for these laboratory testing), cholesterol, triglycerides, high density lipoprotein, sodium, potassium, chloride, bicarbonate, lactate dehydrogenase, uric acid.
Urinalysis:	pH, specific gravity, blood, glucose, protein, ketones, leukocyte esterase, nitrite, total bilirubin, urobilinogen.
Pregnancy test (urine):	For women of childbearing potential only.
Urine drug screen:	Amphetamines, barbiturates, benzodiazepines, cocaine, opiates, methamphetamine, methadone, phencyclidine, and tetrahydrocannabinol.
Alcohol test (breathalyzer):	Ethanol.

A central laboratory will be used to process all hematology, clinical chemistry, and urinalysis samples. Drug screens, alcohol tests, and pregnancy tests will be conducted at the study sites. A breathalyzer alcohol test will be performed at Visit 1 and Visit 3. Details on sampling, handling, and storage of samples will be given in a separate laboratory manual.

#### **10.3.2.1.2 Specimen Handling Requirements**

The transmission of infectious agents may occur through contact with contaminated needles and blood or blood products. Consequently, appropriate blood and body fluid precautions should be employed by all study personnel involved in the collection of blood and handling of specimens in both the clinic and laboratory settings. Refer to current recommendations of the appropriate authorities.

In addition to appropriate handling of subject samples, specific regulations exist regarding the shipment of biologic/etiological samples. Procedures and regulations for the packaging and shipping of biological samples are outlined in the HP-5000-US-07 laboratory manual. The investigator is

responsible for ensuring that all study samples that are to be transported to another location are appropriately packed and shipped according to the applicable regulations.

### **10.3.2.2 Clinical Examinations**

#### **10.3.2.2.1 Vital Signs, Weight and Height**

Vital signs, including heart rate, respiratory rate, temperature, and supine blood pressure will be measured at designated time points. Blood pressure will be measured with the subject in the supine position only. The supine blood pressure should be measured after the subject has been lying down for 5 minutes. Weight (kg) and height (cm) will also be measured.

#### **10.3.2.2.2 Electrocardiogram**

The 12-lead ECG will be a complete, standardized recording and will be performed at designated time points after the subject has been in a supine position for at least 5 minutes before the 12-lead ECG is obtained. All ECG recordings will be identified with the subject number, initials, date, and time of the recording and will be attached to the subject's eCRF. ECG parameter values and interpretation of results will be captured in the eCRF.

#### **10.3.2.2.3 Physical Examination**

The following physical examination will be performed at designated time points before potential exposure to study drug and at the completion of exposure.

- General Appearance
- Head/ Face
- Eyes/ Fundoscopy
- Ears/Hearing
- Nose
- Mouth, Teeth and Throat
- Neck & Thyroid
- Chest/Lungs
- Abdomen
- Skin, Hair, and Nails
- Musculoskeletal: Extremities, Spine
- Vascular/Circulatory
- Lymphatic
- Psychiatric/Behavior
- Brief neurologic

### **10.3.2.3 Adverse Events**

The definitions and management of and special considerations for AEs are provided in [Section 11](#).

### **10.3.2.4 Evaluations of Patch and Dermal Assessment**

Safety dermal characteristics will be assessed using a 5-point numerical scale of adhesion, Berger and Bowman scale of Irritation, 5-point numerical scale of Discomfort.

#### **10.3.2.4.1 Patch Adhesion**

Patch adhesion will be assessed in 2 ways: in-clinic and at-home. At each clinic visit, patch adhesion will be assessed by the investigator or a designee (who will be a trained medical professional such as a nurse practitioner or physician assistant) using the following 5-point numerical scale:

- 0 =  $\geq 90\%$  adhered (essentially no lift off the skin).
- 1 =  $\geq 75\%$  to  $< 90\%$  adhered (some edges only lifting off of the skin).
- 2 =  $\geq 50\%$  to  $< 75\%$  adhered (less than half of the system lifting off of the skin).
- 3 =  $< 50\%$  adhered but not detached (more than half the system lifting off of the skin without falling off).
- 4 = patch detached (patch completely off the skin).

During the Double-blind Treatment Phase at home, subjects will report on any incidence of unscheduled patch detachment, the time and the reason and record in the eDiary. When subjects replace the patch, subjects will complete a questionnaire about adhesion and residue in the eDiary to confirm the following:

- Is the patch 100% attached to the skin? If No, is more than half of the patch still attached?
- Is there any residue on your skin after removing the patch?

#### **10.3.2.4.2 Irritation**

At each clinic visit, the application site where the previous patch was applied will be examined for signs of skin irritation. All subjects will be evaluated by a trained investigator or designee using the Berger and Bowman scale as described below.

Half grades will not be assigned if reactions fall between the unit grades, rather, the more severe of the 2 grades will be assigned.

Dermal response score will be rated on a 0 to 7 scale, whereby 0 is rated as “No evidence of irritation” and 7 is rated as “Strong reaction spreading beyond test (application) site.”

#### **Dermal Response**

- 0 = no evidence of irritation
- 1 = minimal erythema, barely perceptible
- 2 = definite erythema, readily visible; minimal edema or minimal papular response
- 3 = erythema and papules
- 4 = definite edema

- 5 = erythema, edema, and papules
- 6 = vesicular eruption
- 7 = strong reaction spreading beyond the application site

Other effects will be scored via a letter scale and a corresponding numeric scale, whereby N is rated as “No effects” and H is rated as “Small petechial erosions and/or scabs.”

### **Other Effects**

- A = slightly glazed appearance
- B = marked glazed appearance
- C = glazing with peeling and cracking
- F = glazing with fissures
- G = film of dried serous exudates covering all or part of the patch site
- H = small petechial erosions and/or scabs
- N = no other observations

During the Double-blind Treatment Phase at home, subjects will complete a questionnaire about skin irritation in the eDiary. Subjects will be asked to report any skin irritation to the site staff. Skin irritation reported by the subjects will be recorded as AEs. The investigator will assess any irritation observed at the patch application site at clinic visits. If the score of the dermal response and other effects are not 0 or N, it will be evaluated as AEs.

The subjects will be instructed to contact to their site and arrange for an unscheduled visit (i.e., site visit or virtual visit using remote video systems if available) when they experience any significant or intolerable irritation at home to manage the dermal reaction and evaluate it using the above scale.

#### **10.3.2.4.3 Discomfort**

Discomfort will be assessed by the investigator or a designee using a predefined discomfort rating scale. The evaluator will ask the subject, “Are you experiencing any discomfort related to the patch?” If the answer is no, the overall level of discomfort will be rated as 0. If the answer is yes, the evaluator will then ask the subject to rate the discomfort as mild, moderate, or severe along with the description of the discomfort (e.g., itching, burning, pain, stinging, soreness, dryness, and other). Any discomfort mentioned should be recorded as AEs and rated as follows:

- 0 = No discomfort
- 1 = Mild discomfort

- 2 = Moderate but tolerable discomfort
- 3 = Severe, intolerable discomfort
- 4 = Patch not present

During the Double-blind Treatment Phase at home, subjects will complete a questionnaire about discomfort in the eDiary. If there is any discomfort, the description (e.g., itching, burning, pain, stinging, soreness, dryness, and other) will be recorded in the eDiary.

Discomfort reported by the subjects will be recorded as AEs.

The subjects will be instructed to contact to their site and arrange for an unscheduled visit (i.e., site visit or virtual visit using remote video systems if available) when they experience any significant or intolerable discomfort at home to manage the dermal reaction and evaluate it using the above scale.

### **10.3.3 QOL**

#### **10.3.3.1 Mini-OA Knee and Hip QOL (Mini-OAKHQOL)**

The 20-item Mini-OA Knee and Hip QOL (Mini-OAKHQOL) has good psychometric properties and can be used for the measurement of QOL in subjects with OA of the lower limbs (see [Section 18.3](#)).

Subjects will complete a questionnaire about QOL at clinical visits.

#### **10.3.3.2 Work Productivity and Activity Impairment Questionnaire for Osteoarthritis (WPAI: OA)**

The Work Productivity and Activity Impairment Questionnaire for Osteoarthritis (WPAI: OA) Knee or Hip is a 6-item validated questionnaire that assesses the impact of OA on absenteeism, presenteeism, work productivity, and activity impairment. Each subscale score is expressed as an impairment percentage (0-100) where higher numbers indicate greater impairment and less productivity. The WPAI: OA is self-administered by the subject and takes less than 5 minutes to complete (see [Section 18.4](#)).

## 11. ADVERSE EVENTS

### 11.1. Definitions

#### 11.1.1 Adverse Events

Per the International Council for Harmonisation (ICH), an AE is any untoward medical occurrence in a clinical investigation subject administered a pharmaceutical product that does not necessarily have a causal relationship with the product. An AE can therefore be any unfavorable and unintended sign (including a new, clinically important abnormal laboratory finding), symptom, or disease, temporally associated with the product, whether or not related to the product.

Pre-existing diseases or conditions will NOT be considered AEs unless there is an increase in the frequency or severity, or a change in the nature of the disease or condition during the Double-blind Treatment Phase (worsening of a pre-existing condition is considered an AE). AEs may also include pre- or post-treatment complications that occur as a result of protocol-mandated procedures (e.g., invasive procedures such as biopsies).

Any medical condition or clinically significant laboratory abnormality with an onset date after signing the Informed Consent and before the time of dosing is considered to be pre-existing, and should be documented as Medical History (and not as an AE). Any new medical condition or clinically significant laboratory abnormality or an exacerbation of a pre-existing condition with an onset date after signing of Informed Consent and after the time of first dosing should be recorded as an AE. Events occurring in subjects treated with placebo will also be considered AEs. However, AEs reported during treatment-free periods before study drug has been administered are not considered AEs; these events are captured on the eCRF as updates to the subject's medical history.

- All AEs encountered during the clinical study will be reported on the eCRF. All AEs, regardless of relationship to study drug or procedure, should be collected beginning from after the start of the study drug. AEs in clinical investigation subjects include any change in the subject's condition. This includes symptoms, physical findings, or clinical syndromes.
- An abnormal laboratory value may be considered an AE if the identified laboratory abnormality leads to any type of intervention whether prescribed in the protocol or not. It is up to the investigator to determine whether an abnormal laboratory value constitutes an AE. If an abnormal laboratory value is caused by a disease process, the disease process and not the laboratory abnormality should be listed as the AE (e.g., if new onset viral

hepatitis is causing elevated ALT, hepatitis should be captured as the AE and not the elevated ALT).

- Examples of laboratory abnormalities, which should be considered as AEs include those which result in withdrawal of the study treatment, withholding study treatment pending some investigational outcome, reduction of dose of the study treatment, or additional concomitant treatment. All laboratory abnormalities considered to constitute an AE should be reported on the appropriate AE page of the eCRF. Laboratory abnormalities do not need to be listed as separate AEs if they are considered to be part of a clinical syndrome that is being reported as an AE. It is the responsibility of the investigator to review all laboratory findings in all subjects. Abnormal values should be commented upon as to clinical relevance or importance on the eCRF or the laboratory report as appropriate. Medical and scientific judgment should be exercised in deciding whether an isolated laboratory abnormality should be classified as an AE.
- Every effort must be made by the investigator to categorize each AE according to its severity and its relationship to the study treatment.

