- i QOL Questionnaire is Mini-OA Knee and Hip QOL (Mini-OAKHQOL) and Work Productivity and Activity Impairment Questionnaire for Osteoarthritis (WPAI: OA).
- j AEs will be collected starting from the first administered dose.
- k Screening visit (Visit 1) will be completed -28 to -10 days prior to Baseline Visit. Washout visit (Visit 2) is at least 3 days after Visit 1 (e.g. If Visit 1 is Day -10, Visit 2 can be scheduled on Day -7). Washout visit (Visit 2) will be completed -14 to -7 days prior to Baseline Visit. Washout Period will be initiated from the Washout Visit (Visit 2). Washout period is for 7 to 14 days.
- l Only for rescue medication.

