## 11.2. Management of Adverse Events

Adverse events will be collected from the time of first dose administration through the Follow-up Visit or Early Termination Visit, whichever occurs first.

Subjects who complete the Double-blind Treatment Phase or terminate early will continue to be monitored for AEs for 30 days from last day for study treatment, unless resolution, they withdraw consent or are lost to follow-up.

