### 11.2.2 Evaluation

#### 11.2.2.1 Severity of Adverse Events

The clinical severity of an AE will be classified as

Mild	Usually transient and may require only minimal treatment or therapeutic intervention. The event does not generally interfere with usual activities of daily living.
Moderate	Usually alleviated with additional specific therapeutic intervention. The event interferes with usual activities of daily living, causing discomfort but poses no significant or permanent risk of harm to the subject.
Severe	Interrupts usual activities of daily living, or significantly affects clinical status, or may require intensive therapeutic intervention.

It is important to distinguish between severe AEs and SAEs. Severity is a classification of intensity whereas an SAE is an AE that meets serious criteria, as described in [Section 11.1.3](#).

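### Protocol 11.1.1 lets pre-treatment complications of mandated procedures count as AEs, yet every collection rule starts at first dose, so a serious washout complication has no clear SAE reporting route

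*Protocol*

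**What the plan says.** Protocol section 11.1.1 (amended protocol) contains both rules.

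- Its second paragraph widens the AE definition: "AEs may also include pre- or post-treatment complications that occur as a result of protocol-mandated procedures". The example given is an invasive procedure such as a biopsy.
- The next paragraph says that a medical condition or notable laboratory finding "with an onset date after signing the Informed Consent and before the time of dosing is considered to be pre-existing", and assigns it to medical history. It closes by repeating that "AEs reported during treatment-free periods before study drug has been administered are not considered AEs", and says such events go onto the eCRF as medical-history updates.
- The bullet that follows fixes the start of collection: "All AEs, regardless of relationship to study drug or procedure, should be collected beginning from after the start of the study drug".

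Two other places give the same start. Section 11.2 says "Adverse events will be collected from the time of first dose administration". Footnote j to the schedule of events says "AEs will be collected starting from the first administered dose".

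On serious events, section 11.2.2.1 states that "an SAE is an AE that meets serious criteria", and section 11.1.3 defines an SAE as an occurrence at any dose. Section 11.2.6.1 requires all SAEs to reach the sponsor within 24 hours whatever their relationship to treatment. It says when SAE collection ends but not when it begins.

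SAP section 11 repeats the medical-history rule and summarizes medical history for the ITT set.

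**The concern.** One sentence admits pre-treatment procedure complications as AEs. The collection rules leave no way to record them as such, and none of them makes an exception for procedures.

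This matters because the trial does things to people before the first patch. It stops their current analgesics, supplies acetaminophen as rescue and draws blood. Section 5.3 itself lists venipuncture among the risks of participation.

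If a serious event follows from one of these steps, the sponsor needs to hear of it promptly as a possible harm of the trial, not find it later among background conditions. The protocol provides for no data safety monitoring board, so reporting from site to sponsor carries more of the load.

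**Working it through.** The plan gives no figure to reproduce here. The check compares the rules and follows one hypothetical event through them.

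1. **Is washout a mandated procedure?** Yes. The opening of protocol section 10 counts stopping prohibited therapy among the study-related procedures that need consent first. Sections 7.1 and 10.1.1.2 require current prescription and OTC analgesics to be stopped for 7 to 14 days, or five half-lives if longer. The washout is not total: acetaminophen rescue up to 2 g/day is allowed outside the last days before Baseline, and aspirin up to 81 mg/day may continue.

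2. **Take a subject hospitalized during washout because of stopping therapy.** Under the second paragraph of 11.1.1 this may be an AE. Under the next paragraph it is medical history and not an AE. Under the bullet, 11.2 and footnote j, AE collection has not begun, and the bullet says that relationship to a procedure makes no difference.

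3. **Is there a separate SAE route?** Section 11.2.2.1 makes an SAE a subset of AEs. An event that is not an AE therefore cannot be an SAE under that definition, and the 24-hour duty in 11.2.6.1 does not clearly attach. Section 11.2.6.1 does not close the gap, because it gives no start at consent.

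4. **Where does the record go?**
   - *Randomized subject:* the eCRF medical-history page, and from there the ITT medical-history table. SAP section 11 does not plan to separate post-consent events from older conditions.
   - *Subject not randomized:* the ITT set (SAP 5.1) requires randomization, and the safety set (SAP 5.2) requires at least one patch. The event enters neither the medical-history summary nor any safety summary.

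5. **How long is the interval?** The first patch is applied at Baseline, so the interval to first dose is the Screening-to-Baseline interval of section 10.1.1.1: 10 to 28 days. The schedule runs to Day 91 after Baseline. The uncovered share of a completer's participation is:
   - shortest: 10 / (10 + 91) = 10/101 = 9.9%
   - longest: 28 / (28 + 91) = 28/119 = 23.5%

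   For a subject who fails screening before the first patch, it is all of it.

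6. **Can the SAP hold such a record?** Yes. Appendix 1 classes an AE that starts before study medication as not treatment-emergent, and SAP 18.1 says the listings cover all AEs. The SAP has a category for pre-dose AEs that the protocol's collection rules leave empty.

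**The case against.** The strongest reply is that the protocol has made a choice and stated it several times. The widening sentence is permissive, and its example is a biopsy, which this trial does not perform. Against it stand two statements in the next paragraph, the bullet, section 11.2, footnote j and SAP section 11. The bullet even addresses procedures directly. On this view sites have a clear instruction, nothing shows that they will diverge, and deleting one sentence would restore consistency.

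Much of this stands. Starting general AE collection at first dose is a legitimate choice, and divergent recording between sites is a possibility, not a finding. But deleting the sentence would settle the wording by making the reporting gap complete.

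A reader might also infer more than the text supports:

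- *That the event is never reported to the sponsor.* Section 11.1.1 sends it to the eCRF as medical history, the IWRS records the date and reason for pre-randomization withdrawals, and section 15.3 requires prompt notice to the IRB of new safety information. What is missing is AE/SAE classification and a clear 24-hour route.
- *That the protocol expressly excludes pre-dose SAEs.* It does not. The gap is inferred from the SAE definition together with the missing start date.
- *That section 11.2 and footnote j turn pre-dose events into medical history.* They set only the start of AE collection. The medical-history rule is in 11.1.1 and SAP section 11.
- *That all analgesics are withdrawn.* Acetaminophen rescue, low-dose aspirin and topical NSAIDs not used on the knees remain available.

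**Conclusion.** The point holds in limited form. The AE definition and the collection rules conflict over pre-treatment complications of mandated procedures, and the conflict reaches the washout. A serious event of this kind has no clear AE or SAE status and no clear 24-hour path, although it should still appear on the eCRF as medical history. For subjects who are not randomized it enters no planned summary.

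The size is a duration, 10 to 28 days per subject, and not a count. The documents give no rate for such events, so no expected number can be stated.

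The conclusion rests on two readings: that washout is a protocol-mandated procedure, which section 10 supports, and that an SAE must first be an AE, which section 11.2.2.1 states. Efficacy results and TEAE tables are not affected. The case for correcting it is subject safety and consistent records.

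**What to change.** Reconcile protocol sections 11.1.1, 11.2, 11.2.2.1 and 11.2.6.1, footnote j of the schedule of events, and SAP section 11 and Appendix 1, so that they agree on when collection starts. Specifically:

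- State that SAEs, and AEs related to protocol-mandated procedures (washout, sponsor-supplied rescue medication, blood draws), are collected from signature of consent.
- Apply the existing 24-hour reporting duty to those SAEs.
- List them separately as pre-treatment and not treatment-emergent, including for subjects who are not randomized.
- Keep other non-serious pre-dose events as medical history.

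The cost is protocol and eCRF wording, one listing, and a few more reports from the screening period. The SAP's existing class for events that are not treatment-emergent can hold the new records.
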